The ablation will be planned and the ablation applicators inserted percutaneously using routine FDG PET/CT and possible supplemental US guidance. The ablation will then be performed using current protocols with either microwave ablation or cryoablation devices. Microwave ablation and cryoablation devices offer complimentary advantages that enable us to safely and effectively treat many liver tumors. Cryoablation may be better tolerated and less painful when ablating liver tumors close to the liver capsule or diaphragm. The iceball created during cryoablation is usually well visualized during the ablation, which can offer safety advantages when ablating near critical structures. Microwave ablation has fewer tendencies to induce thrombocytopenia or myoglobinemia than cryoablation, which can be an advantage in patients with baseline thrombocytopenia or renal insufficiency. Microwave ablation is better able to overcome vascular heat-sink phenomena that can limit the ablation of tumor cells abutting large blood vessels. Our standard practice is to choose the most appropriate ablation technology based on the individual patient's specific circumstances. Radiofrequency ablation is not included in this protocol, as microwave ablation has almost completely replaced the use of radiofrequency ablation in our practice.

[figure not shown]
When the initial ablation is completed, intra-procedural AP-PET-1 (research scan #1) will be performed and the findings recorded. Specifically, the ablation margin separating the FDG-avid tumor from the normal ammonia-perfused liver will be assessed for visibility and thickness along the entire circumference. Patients with adequate renal function (EGFR >60) will then undergo intra-procedural contrast-enhanced CT, as is now performed in routine clinical practice to monitor initial results. Non-contrast CT will be used in cases of inadequate renal function or contrast allergy. If no additional overlapping ablation applications are deemed necessary or appropriate based on routine CT (Pathway 1), the procedure will be concluded at this point. AP-PET information may be used to aid the margin assessment if CT is inconclusive. Note that routine CT will always be used to determine the safety of additional overlapping ablation, per routine clinical practice. This is because proximity of ablation devices to critical structures can only be imaged with CT and not with PET. The patient will then undergo routine 24-hour post-procedure liver MRI

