CONFIDENTIAL

This document is confidential. Do not disclose or use except as authorized.

or CT. If the CT scan suggests an inadequate ablation margin of less than 5-10 mm at any portion of the tumor surface, additional ablations will be applied to the under-treated areas (Pathway 2), if deemed safe and appropriate based on standard clinical practice. Then, AP-PET-2 will be repeated (research scan #2). Not more than two AP-PET scans will be performed during the entire procedure. The AP-PET scan(s), illustrated schematically below, constitute the only research component of the protocol.

Arm 2: Arm 2 will not include the option of AP-PET 2 (research scan #2) due to the longer half-life of FDG.

The devascularized ablation zone contains trapped high tumor FDG activity and low ablation margin FDG activity, whereas normal liver is perfused with high activity ¹³N-ammonia. The relatively photopenic ring around the tumor confirms the presence of an adequate ablation margin.

For patients with FDG-avid tumors, visibility rates of the entire ablation margin using AP-PET-1 will be compared to the visibility rates of the entire ablation margin using the intra-procedural CECT scan. Visibility rates using AP-PET-1 will also be compared to the visibility rates using the intra-procedural CECT scan fused to FDG PET (FDG PET/CECT). The concordance rates of the final intra-procedural AP-PET (research scan #1 or #2) with gold standard 24-hour post-procedure MRI or CT will be determined.

For those patients with non-FDG-avid tumors, retrospective software fusion of AP-PET-1 with pre-procedural MRI or CT will be used to assess visibility rates of the ablation margin and will be compared with visibility rates of the ablation margin using retrospective fusion of the intra-procedural CECT and pre-procedural MRI or CT. Similarly, in patients with non-FDG-avid tumors the concordance rate of final intra-procedural AP-PET (research scan #1 or #2) fused to pre-procedural MRI or CT, with gold standard 24-hour post-procedure MRI or CT will be determined. The analysis of AP-PET utility in patients with non-FDG-avid tumors is a secondary objective of this study, but is nevertheless of interest, as AP-PET may prove valuable in these patients who cannot receive IV contrast or

CONFIDENTIAL

This document is confidential. Do not disclose or use except as authorized.

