1.2 Primary Objectives

Arm 2: The primary and secondary objectives are identical for Arms 1 & 2 of the study (except that in Arm 2, no research scan #2 will be performed).

- 1. For FDG-avid tumors, compare the rates of complete, circumferential ablation margin visibility during FDG PET/CT-guided liver ablations using two imaging techniques: intra-procedural AP-PET-1 (research scan #1) and intra-procedural CECT. Discordance rates for complete ablation margin visibility between the two imaging techniques will be calculated.
- 2. For FDG-avid tumors, compare the rates of complete, circumferential ablation margin visibility during FDG PET/CT-guided liver ablations using two imaging techniques: intra-procedural AP-PET-1 and intra-procedural CECT fused with FDG PET (FDG PET/CECT). Discordance rates for complete ablation margin visibility between the two imaging techniques will be calculated.
- 3. In assessing adequacy of the ablation margin for FDG-avid tumors, the concordance rates of final intra-procedural AP-PET (research scan #1 or #2) with gold standard 24-hour post-procedure MRI or CT will be determined. (Includes patients with renal insufficiency who cannot receive intra-procedural iodinated IV contrast.)
- 4. For non-FDG-avid tumors, compare the rates of complete, circumferential ablation margin visibility during FDG PET/CT-guided liver ablations using two imaging techniques: 1) intra-procedural AP-PET-1 fused to pre-procedural MRI or CT and 2) intra-procedural CECT fused to pre-procedural MRI or CT. Discordance rates for complete ablation margin visibility between the two imaging techniques will be calculated.
- 5. In assessing adequacy of the ablation margin for non-FDG-avid tumors, the concordance rate of final intra-procedural AP-PET (research scan #1 or #2) fused to pre-procedural MRI or CT with gold standard 24-hour post-procedure MRI or CT will be determined. (Includes patients with renal insufficiency who cannot receive intra-

CONFIDENTIAL

This document is confidential. Do not disclose or use except as authorized.

procedural iodinated IV contrast.)

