- Current techniques for intra-procedural assessment of tumor ablation margins have limitations. For example, when performing CT-guided ablations, it is standard practice to obtain an intra-procedural contrast-enhanced CT (CECT) to monitor whether the tumor is being treated fully and an adequate ablation margin is being obtained following thermal ablation. CECT is usually performed only once near the end of the procedure since one dose of IV contrast material is usually the limit for a 24-hour period. If a reduced dose of IV contrast is used, this may allow for two intra-procedural CECT scans, however, this may limit the effectiveness of the method. For example, the degree of liver enhancement is reduced making it difficult to distinguish tumor from liver. Patients with a contrast material allergy or severe renal insufficiency (EGFR < 30) are often not considered candidates for CECT. An additional limitation of CECT in the assessment of liver tumor ablations is that once ablated, the tumor is usually difficult to distinguish from the surrounding ablated normal liver tissue. Consequently, direct visualization of the ablation margin is often not possible using CECT. US is even less effective in assessing ablation results in that tumor visibility is rapidly obscured by the developing ablation zone and the ablation zone margins are usually indistinct. For liver tumors, MRI performs better in depicting not only the exact borders of the ablation zone, but also in showing the residual tumor. As a result, 24-hour follow-up MRI with contrast can be an effective method for confirming the thickness or size of the ablation margin. Follow-up MRI, however, does not allow for intra-procedural assessment of ablation results during US, CT, or PET/CT-guided ablations that might prompt immediate further treatment while the patient is still on the scanner table.
- An effective imaging technique for monitoring ablations that can be safely performed repeatedly during ablation procedures is needed.
- We have previously shown that, during PET/CT-guided tumor ablation procedures, tumor FDG activity is not dissipated by thermal ablation, whether through heating or freezing (2). Tumor FDG activity remains unperturbed following ablation allowing for continued excellent PET visibility of the tumor for hours after the procedure. This unique feature of PET imaging can potentially be used to help monitor the thickness of the ablation zone

CONFIDENTIAL

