depicted as a “cold” rim would either be absent or incomplete, indicating an inadequate ablation margin. AP-PET would be obtained using a radiopharmaceutical administration protocol identical to our standard cardiac practice. PET image acquisition will be obtained dynamically, as the N-13 ammonia is injected intravenously, using 15 second frames over 5 minutes.

- The advantages of using AP-PET to define the adequacy of the ablation zone margin include a very low radiation dose to the patient, substantially less than a diagnostic CT scan and approximately one-tenth the dose from FDG PET, using equal administered activity (9). AP-PET is thus an ideal intra-procedural monitoring method that can be used repeatedly. Incorporating CECT into the PET/CT protocol could be used to assess the ablation zone margin relative to the FDG-avid tumor, but is subject to the problem of misregistration of the PET and CT images (3). In other words, the PET and CT components of a PET/CT scan are acquired at different time points and may not line up perfectly with each other, for example, due to respiratory motion between the PET and CT scans. Using FDG PET to visualize the ablated tumor and AP-PET to visualize the perfused tissue eliminates the issue of misregistration, since both are imaged at the same time and in the same position using a single PET scan.
- **Arm 2:** The advantages of using FDG as the perfusion agent for the AP-PET scan include that it does not require an on-site cyclotron – thus the technique has the potential for wide applicability. FDG is used in clinical practice during tumor ablation procedures in a split-dose fashion, dividing a standard dose into two parts: one for the targeting phase of the procedure and one for the final assessment phase of the procedure. This keeps the total radiation dose within that of a standard diagnostic PET/CT scan.
- Our Nuclear Medicine physicists at BWH have performed a PET/CT phantom study (see images below) that created compartments simulating the expected radioactivity concentrations in normal liver, the ablation margin, and the tumor that support the potential of AP-PET to demonstrate the ablation margin of FDG-avid tumors even with acquisitions as short as 30 seconds. The ablation margin appears as a dark ring around the FDG-avid tumor. Surrounding normal liver remains perfused by activity.

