14. STATISTICAL CONSIDERATIONS

14.1 Study Design/Endpoints

Arm 2: Study design/endpoints are identical for Arms 1 & 2.

In this study of patients with liver lesions, it is expected that roughly two-thirds of patients will have FDG-avid tumors, one-third of patients will have non FDG-avid tumors, and although it is possible for a patient to have both types of tumor, that is considered rare. For sample size and power considerations we therefore conservatively assume that patients will have one type of tumor or the other and therefore target a sample size of 100 patients per arm, allowing for the potential for renal insufficiency in up to 25% of all patients (described in more detail below). Also, as the techniques focus on analysis by tumor and it is estimated that 70% of patients will have only a single lesion, the sample size considerations will focus on enrolling *patients* rather than *tumors*. Multiple tumors per patient, when they occur, will be treated and assessed in the statistical analysis, with appropriate adjustment for clustering of tumors within a patient to account for correlation of responses within a patient. Sample size considerations, however, focus on enrollment of patients. The study design and endpoints are identical for Arm 1 and Arm 2.

Primary Objectives:

1. Among FDG-avid liver tumors, comparison of imaging techniques will be done on paired tumor samples using McNemar's test, focusing on discordant pairs (AP-PET-1 adequate/CECT inadequate and AP-PET-1 inadequate/CECT adequate). For these comparisons it is expected that the rate of discordance will be high (near 60% of all pairs) and that differential in discordance will be large (difference between discordant pairs on the order of 50% or higher). In addition to comparing discordant pairs, there is interest in being able to precisely estimate the visibility rates under each imaging modality. With 50 paired samples in the FDG-avid liver tumor ablation group in each arm, visibility of the entire ablation margin can be estimated with a 95% binomial confidence interval that should be no wider than 24 percentage points (+/- 12%) in the expected range of visibility of each modality (80% for AP-PET and 20% for CECT). This sample size will provide greater than 90% power for McNemar's test using a 5% type I error given the assumptions above about discordance.

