3. In patients with FDG-avid liver tumors, the goal of this objective is to assess the proportion of cases confirmed to have adequate ablation margins using 24-hour MRI or CT as the gold standard among those identified as nominally adequate at the time of final intra-procedural imaging. Note that for this objective, patients do not have to receive intra-procedural iodinated IV contrast, hence the reduction in sample size due to renal insufficiency does not apply to this objective. It is expected that nearly 95% of cases will be identified as nominally adequate by all available post-ablation intra-procedural imaging data (i.e. standard-of-care imaging plus AP-PET). With 75 cases per arm, this translates to roughly 71 nominally adequate cases. Among these cases, the ablation margin adequacy rates based on 24-hour MRI or CT will be estimated with 95% binomial confidence intervals and it is expected that the adequacy rates for all available post-ablation intra-procedural imaging will be high, in the range of 90% or higher. With the sample size stated above, the 95% confidence intervals to confirm adequate ablation after 24 hours will be no wider than 16 percentage points (+/- 8%). It is also of interest to confirm that margins that were deemed inadequate on AP-PET alone were confirmed inadequate based on 24-hour MRI or CT but this objective is largely exploratory since the sample size for cases labeled inadequate after AP-PET is expected to be very low, only 5% of the total cases. Finally, it is of interest to assess agreement of final intra-procedural AP-PET with 24-hour MRI or CT. Concordance rates are unknown but are estimated to be in the range of 50 to 80%. With 75 cases per arm, the 95% confidence intervals on the concordance rates are expected to be no wider than 24 percentage points (+/- 12%) assuming, conservatively, that the true concordance rate is near 50%.

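### As written, Arm 2's only perfusion PET precedes any CT-triggered re-ablation, so for re-ablated tumours its concordance with the 24-hour scan compares two different ablation zones

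*Combined protocol and SAP*

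**What the plan says.** Section 1.1 fixes the order of events: "When the initial ablation is completed, intra-procedural AP-PET-1 (research scan #1) will be performed and the findings recorded". Routine CT comes next. If CT suggests too thin a margin, and more ablation is judged safe and appropriate, the under-treated areas are ablated again (Pathway 2). In Arm 1 the perfusion PET is then repeated. For Arm 2, "Arm 2 will not include the option of AP-PET 2 (research scan #2) due to the longer half-life of FDG". Section 5 confirms that Arm 2 has a single perfusion scan, and the opening of Section 1.1 says that the protocol is the same in every other respect.

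The objectives were not adapted. Section 1.2 carries them over to Arm 2 with one qualification, "except that in Arm 2, no research scan #2 will be performed", and Section 14.1 says: "The study design and endpoints are identical for Arm 1 and Arm 2". Primary Objectives 3 (FDG-avid) and 5 (non-FDG-avid) in Section 1.2 ask for the concordance of the final perfusion PET with 24-hour MRI or CT. Section 14.1 takes this up last under each objective; for Objective 3, "it is of interest to assess agreement of final intra-procedural AP-PET with 24-hour MRI or CT". It expects concordance of 50 to 80%, with intervals of ±12 points on 75 cases and ±18 points on 33.

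The Arm 2 paragraph of Section 2.3 describes clinical practice as splitting the FDG dose, "one for the targeting phase of the procedure and one for the final assessment phase of the procedure".

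**The concern.** In Arm 1, taking scan #1 or #2 as the final scan keeps the PET and the 24-hour scan on the same ablation zone. In Arm 2 the final scan is always scan #1. For a tumour ablated again after it, the PET shows the zone before that ablation and the 24-hour scan shows the zone after it. Nothing in the plan excludes, flags or separates these tumours.

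Their concordance then mixes diagnostic error with the effect of treatment. A correct inadequate read followed by successful re-ablation is scored as a disagreement. That is also the benefit to the patient that Section 2.3 hopes for. Because Section 1.1 lets the PET inform the decision when CT is inconclusive, a correct read can help to bring about its own apparent error. In the other direction, a wrong adequate read that CT corrects through further ablation is scored as an agreement.

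The same mismatch enters the exploratory check that inadequate reads are confirmed at 24 hours, and the secondary estimates of local progression by PET adequacy.

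**Working it through.** **1. Sequence in each arm (Sections 1.1 and 5).**

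| Step | Arm 1 | Arm 2 as written |
|---|---|---|
| Initial ablation | yes | yes |
| Perfusion PET #1 | yes | yes (FDG) |
| Routine CT, decision | yes | yes |
| Further ablation if CT margin inadequate | Pathway 2 | Pathway 2 |
| Perfusion PET #2 after further ablation | yes | no |
| 24-hour MRI or CT | final zone | final zone |
| Zone on the final PET, re-ablated tumour | final zone | earlier zone |

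**2. Scoring of a re-ablated Arm 2 tumour when re-ablation succeeds (24-hour scan adequate).**

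| PET #1 read | Correct for its own zone? | Scored as |
|---|---|---|
| inadequate | yes | discordant (false disagreement) |
| adequate | no | concordant (false agreement) |
| inadequate | no | discordant |
| adequate | yes | concordant |

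The first two rows distort the rate, in opposite directions. The first row also drives the exploratory check: if every inadequate read were right and every such tumour successfully re-ablated, none would be confirmed.

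**3. The plan's own precision.** Half-width = 1.96 × √(0.5 × 0.5 / n).
- n = 75: 11.3 points (exact binomial 11.8), against ±12 stated.
- n = 33: 17.1 points (exact 17.8), against ±18 stated.

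Both stated figures reproduce.

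**4. Why the effect cannot be sized.** Let r be the share of tumours re-ablated, c the concordance that same-zone scans would have given, s the share of re-ablated tumours read inadequate on PET #1, and g the share of them adequate at 24 hours. Treat the read and the 24-hour result as independent within re-ablated tumours.

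Measured concordance = (1 − r) × c + r × k, with k = s × (1 − g) + (1 − s) × g.

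Take g = 0.9, borrowed from the plan's expectation for nominally adequate cases. The values of r and s are assumptions; those of c are the ends of the plan's 50 to 80% range.

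| c | s | k | r = 10% | r = 20% |
|---|---|---|---|---|
| 80% | 0.8 | 0.26 | 74.6% | 69.2% |
| 50% | 0.5 | 0.50 | 50.0% | 50.0% |
| 50% | 0.2 | 0.74 | 52.4% | 54.8% |

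For example, the first row at r = 20% is 0.8 × 0.80 + 0.2 × 0.26 = 0.692. The shift at r = 20% runs from −10.8 points through zero to +4.8. These rows illustrate; they are not bounds.

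**5. The 5% in Section 14.1 does not supply r.** Under Objectives 3 and 5 it is the complement of the 95% expected to be adequate at the end of the procedure on all available imaging, so it is not the share that CT sends to Pathway 2. Nor does it fit as the share of PET reads that are inadequate. If 95% were read adequate on PET and at least 90% of those confirmed, concordance would be at least 0.95 × 0.90 = 85.5%, above the 50 to 80% the plan expects.

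**6. Precision if re-ablated tumours are set apart** (formula of step 3; the 20% is assumed).

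| Starting n | Half-width | n after 20% set apart | Half-width |
|---|---|---|---|
| 75 (Objective 3 text) | 11.3 | 60 | 12.7 |
| 67 (FDG-avid target, Objective 1 text) | 12.0 | 54 | 13.3 |
| 33 (Objective 5 text) | 17.1 | 26 | 19.2 |

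The ±12 needs at least 67 cases and the ±18 at least 30. So ±12 survives setting apart up to 8 of 75 (about 11%) but none of 67, and ±18 survives 3 of 33 (9%).

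**The case against.** The strongest reply is that the timing is not settled. Section 2.3, in its Arm 2 paragraph, links the second part of the FDG dose to the final assessment phase, and Section 6 calls dose splitting standard clinical practice. If the research scan was in fact done after the last ablation, Objectives 3 and 5 have no mismatch. This stands as a doubt but does not overturn the reading. The sentence describes clinical practice, whereas Section 1.1 says that Arm 2 only exchanges the tracer. A scan done last would also move the problem: since "CECT is usually performed only once near the end of the procedure", the PET/CT pairs of Objectives 1, 2 and 4 could then show different zones for re-ablated tumours.

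Second, the reach is limited, and this stands. Concordance is estimated with an interval, without a test or threshold. The check of inadequate reads is called largely exploratory, the progression summary has no formal comparison, and Section 1.1 calls the non-FDG-avid analysis secondary. In Section 14.1 the stated goal of Objectives 3 and 5 is 24-hour adequacy among cases judged adequate at the end of the procedure on all available imaging, which does not depend on the PET read alone.

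Third, tumours with no later ablation are a selected group, because those in which CT found under-treatment have been taken out. This also stands. Their rate is not an unbiased measure of agreement for all tumours and cannot replace the all-case rate.

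**Conclusion.** The point holds for Arm 2 tumours ablated after their only perfusion PET, on the sequence as written. For those tumours the concordance in Objectives 3 and 5 cannot be read as diagnostic agreement. The exploratory check and the progression estimates carry the same flaw. Where it occurs, the error is systematic and the confidence interval does not cover it.

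Two stronger conclusions are tempting. A reader might infer that Arm 2 concordance is biased downwards, or that the shift is capped at about 5 points because 5% of cases are expected to be inadequate. The documents support neither: the two false scorings pull in opposite directions, no re-ablation rate is given, and the 5% refers to final imaging. A reader might also infer that the Arm 2 primary objectives fail as a whole. They do not. Objectives 1, 2 and 4, as sequenced, pair PET #1 with the CT taken before further ablation, and 24-hour adequacy among nominally adequate cases is not affected in this way.

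This should be corrected in the analysis and reporting. It does not invalidate the arm.

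**What to change.** 1. Record for each Arm 2 tumour whether any ablation followed its perfusion PET, from the actual order of events. This also settles the timing question. The front sheet shows accrual permanently closed in March 2018, so clarifying the protocol text can no longer change conduct.
2. For Objectives 3 and 5, the check of inadequate reads and the progression summary, report Arm 2 results separately for tumours with and without later ablation, beside the all-case rate.
3. State how to read them: the rate without later ablation is same-zone agreement in a selected group, and the rate in re-ablated tumours is not diagnostic agreement.

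The cost is one yes/no item per tumour, one extra table and the modest loss of precision in step 6 of the working. No new patients or scans are needed.

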1.3 Secondary Objectives

- 1. For FDG-avid tumors, rates of local tumor progression based on a minimum of 3-12 month imaging follow-up will be compared for ablation margin adequacy assessed by blinded retrospective reads of final intra-procedural AP-PET (research scan #1 or #2) and 24-hour post-procedure MRI or CT. (Includes patients with renal insufficiency who cannot receive intra-procedural iodinated IV contrast.)

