4. Among non FDG-avid tumors (expected to be one-third of patient accrual) comparison of imaging techniques will be done on paired samples using McNemar's test, focusing on discordant pairs (AP-PET fused to pre-procedural MRI or CT adequate/CECT fused to pre-procedural MRI or CT inadequate and AP-PET fused to pre-procedural MRI or CT inadequate/CECT fused to pre-procedural MRI or CT adequate). For these comparisons it is expected that the rate of discordance will be high (near 70% of all pairs) and that differential in discordance will be large (difference between discordant pairs on the order of 60%). In addition to comparing discordant pairs, there is interest in being able to precisely estimate the visibility rates under each imaging modality. With 25 paired samples per arm in the non FDG-avid liver tumor ablation group, visibility of the entire ablation margin can be estimated with a 95% binomial confidence interval that should be no wider than 34 percentage points (+/- 17%) in the expected range of visibility of each modality (80% for AP-PET and 20% for CECT). This sample size will provide greater than 90% power for McNemar's test using a 5% type I error given the assumptions above about discordance.

CONFIDENTIAL

This document is confidential. Do not disclose or use except as authorized.

Since both imaging modalities are required for McNemar's test and the rate of renal insufficiency that would preclude a paired CECT scan is estimated to be roughly 25%, inflation for loss due to patients with renal insufficiency implies that the non FDG-avid tumor target sample size for this trial is 33 patients per arm ($=25/0.75$). The trial will be monitored closely for potential early closure if the rate of renal insufficiency is lower than 25% or potential extension of accrual if the yield of paired samples is lower than 75%.

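### Non-FDG-avid comparison is secondary in 1.1 but primary in 1.2 and 14.1; Objectives 1 and 4 each get a 5% McNemar test with no order or success rule, up to about 9.8% per arm if either can carry a primary claim

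*Combined protocol and SAP*

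**What the plan says.** The status of the non-FDG-avid analyses differs between sections.

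- Section 1.1 (Study Design - Abstract): "The analysis of AP-PET utility in patients with non-FDG-avid tumors is a secondary objective of this study".
- Section 1.2 (Primary Objectives), item 4: "For non-FDG-avid tumors, compare the rates of complete, circumferential ablation margin visibility during FDG PET/CT-guided liver ablations using two imaging techniques". Item 5 is the matching concordance analysis against 24-hour MRI or CT.
- Section 1.3 (Secondary Objectives) has one entry, and it does not concern non-FDG-avid tumors: "For FDG-avid tumors, rates of local tumor progression based on a minimum of 3-12 month imaging follow-up will be compared".
- Section 14.1 places items 1 to 5 under its primary heading and opens its secondary heading only after item 5. Item 4 reads: "Among non FDG-avid tumors (expected to be one-third of patient accrual) comparison of imaging techniques will be done on paired samples using McNemar's test".

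Both comparisons are planned as tests. For Objective 1 and again for Objective 4, section 14.1 claims "greater than 90% power for McNemar's test using a 5% type I error". Objective 1 rests on this yield: "With 50 paired samples in the FDG-avid liver tumor ablation group in each arm". Objective 4 rests on 25 pairs per arm. Sections 1.2 and 14.1 apply the same objectives and endpoints to both arms. I found no testing order, division of alpha, multiplicity statement or rule saying which primary objective decides the study.

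**The concern.** The label determines what a split result means. Suppose that in one arm Objective 1 is not significant and Objective 4, on 25 pairs, is. Under 1.2 and 14.1 a primary objective has been met. Under 1.1 the main comparison has failed and a secondary one is positive. Nothing in the plan chooses between these readings, so the choice could be made after the results are known.

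If both comparisons are primary and either may carry a claim, each arm has two chances of a false rejection, each at the full 5%. The error rate attached to a primary claim in an arm would then exceed the 5% quoted for each test.

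**Working it through.** **Inputs, all from 14.1**
- Objective 1: 50 pairs per arm; "rate of discordance will be high (near 60% of all pairs"; difference between the two discordant cells about 50 points. The cells are therefore 0.55 and 0.05.
- Objective 4: 25 pairs per arm; 70% discordant; difference about 60 points. The cells are 0.65 and 0.05.
- Type I error 5% for each test.
- For planning, each patient is assumed to have one tumor type or the other, so the two tests use different patients and can be treated as independent.

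**Step 1. Reproduce the plan's power (two-sided 5%)**

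Normal approximation: power = Φ[(d√n − 1.96√p) / √(p − d²)], with p the discordant fraction and d the difference.
- Objective 1: (0.50√50 − 1.96√0.60) / √(0.60 − 0.25) = 3.41, power 99.97%. Exact test, by enumeration: 99.95%.
- Objective 4: (0.60√25 − 1.96√0.70) / √(0.70 − 0.36) = 2.33, power 99.0%. Exact test: 98.4%.

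Both agree with the plan's statement of more than 90%.

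**Step 2. Chance of at least one false rejection within an arm, either direction**

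Formula: 1 − (1 − α₁)(1 − α₄).

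| Version of the test | Size, Objective 1 | Size, Objective 4 | Per arm |
|---|---|---|---|
| Nominal | 5% | 5% | 1 − 0.95² = 9.75% |
| Exact McNemar | 3.05% | 3.06% | 6.0% |
| Asymptotic McNemar | 5.21% | 5.10% | 10.0% |

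The last two rows use attained sizes enumerated under the null with the planned discordance (60% of 50 pairs, 70% of 25 pairs). The plan does not name the version.

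**Step 3. False claim that AP-PET is superior**

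The plan does not state sidedness. If the tests are two-sided at 5%, each has 2.5% in the direction favoring AP-PET. One test gives 2.5%; two give 1 − 0.975² = 4.9% per arm. If they are one-sided at 5%, the figures are 5% and 9.75%.

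**Step 4. Power if Objective 4 is tested only after a significant Objective 1**

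With exact tests and independent cohorts, 0.9995 × 0.9839 = 0.9834, against 0.9839 without the gate: a loss of about 0.05 percentage points.

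If Objective 1 reached only 25 pairs, its exact power would be 93.7%. Were Objective 4 still to have its own 25 pairs, its gated power would be 0.937 × 0.984 = 92.2%, a loss of about 6 points.

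**The case against.** The best defense is that the plan never says one significant test makes the study a success. Objectives 1 and 4 concern different tumor types and different image comparisons: AP-PET against CECT in one, both fused to pre-procedural imaging in the other. Separate claims in separate populations can reasonably be reported at 5% each. Much of 14.1 is also estimation, since Objectives 2, 3 and 5 have confidence intervals only.

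This stands in part. The either-test rule is inferred from the plan's silence, so the error rates are conditional on it, and a fixed sequence is one defensible choice and not something the documents require. The defense does not remove the conflict between 1.1 and 1.2/14.1, or tell the reader how to classify a result positive on Objective 4 alone.

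Two stronger readings are tempting and go too far:

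- A reader might count four tests over both arms and quote 1 − 0.95⁴ = 18.5%. Section 1.1 describes the arms as independent and non-randomized, with different tracers, and no claim pooled across them is planned. Error control within each arm is defensible, so 18.5% is not a rate this plan must control.
- A reader might say AP-PET can be declared superior at nearly twice the quoted 5%. That holds only for one-sided tests at 5%. With two-sided tests the rate is about 4.9% per arm: nearly double the 2.5% of a single test, but not above 5%.

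**Conclusion.** The contradiction is established from the current text: the same analyses are secondary in 1.1 and primary in 1.2 and 14.1, and nothing reconciles them. Two 5% tests therefore stand without an order or a success rule.

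The size is moderate. If either test can support a primary claim, the either-direction error within an arm is up to about 9.8% at nominal size, in a range of about 6% to 10% by test version. This assumes independent cohorts and, for the attained sizes, the planned discordance. The documents do not support saying that the study will be judged on whichever cohort succeeds; they leave that open, and that gap is the defect. The planned power figures are not in dispute. The point should be corrected because it governs what may be reported as a primary success, and the correction is inexpensive.

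**What to change.** Make 1.1, 1.2 and 14.1 agree:

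1. Name Objective 1 as the confirmatory test in each arm.
2. List Objectives 4 and 5 as secondary, in line with 1.1, and add them to 1.3.
3. Test Objective 4 at 5% only if Objective 1 in the same arm is significant. Otherwise report it as an estimate with its confidence interval.
4. State whether the tests are one- or two-sided and which version of McNemar's test is used.
5. State that each arm keeps its own 5%.

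The front sheet records closure to accrual, but the change still governs analysis and publication. It should be dated, with a statement of whether any comparative results had been seen.

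**Cost.** Wording only: no additional patients or scans. With the planned pairs, Objective 4 power stays at about 98%, a loss below 0.1 percentage point. The real price is that no formal Objective 4 claim is available in an arm where Objective 1 fails. That price rises if far fewer pairs are obtained, as the 25-pair calculation shows.
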